**A RCT of Outreach and Inreach Strategies for Boosting
CRC Screening in a Federally-Qualified Health Center**

NCT02870049

Document Date: 09/01/2015

SPECIFIC AIMS

Colorectal cancer (CRC) screening has the potential to save lives, but is underutilized, particularly among underserved populations. For example, screening rates among Latinos are just 40%, and among uninsured and those insured by Medicaid are just 20 and 25%, respectively. Low rates for Latinos are of particular concern, as they have higher than average stage at presentation and stage-specific mortality than non-Latino whites. To reduce CRC disparities, interventions to optimize screening among underserved populations, particularly among Latinos, are required. Federally Qualified Community Health Centers (FQHCs) are in a unique position to leverage their service to underserved populations to deliver the benefits of CRC screening for several reasons. FQHCs traditionally serve the uninsured, underinsured, and racial/ethnic minorities that have traditionally low rates of being up-to-date with cancer screening, and are now required to publically report screening rates due to federal mandates. For example, San Ysidro Health Center, Inc. (SYHC) is a large FQHC that includes a network of 10 clinic sites that serves over 90,000 patients annually, who come from a predominantly low-income, Spanish-speaking Latino population in the U.S.-Mexico border region of San Diego County; in 2013 the publicized CRC screening rate was just 31%. While low rates of screening at FQHCs such as SYHC are of great concern, provisions within the Affordable Care Act, such as new access to health insurance for populations that commonly utilize FQHCs, may offer a historic opportunity to develop and implement strategies for optimizing screening rates for underserved populations, including low income Latinos. In 2013, SYHC approached UCSD and SDSU partners on how to build a CRC screening infrastructure to increase screening rates.

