Examples of successful outreach approaches have included use of mailed invitations with telephone follow up to promote screening fecal occult blood test (FOBT) completion, as well as patient navigation to promote colonoscopy completion. We conducted a randomized, comparative effectiveness trial of the impact three system-level strategies—usual care, mailed invitation to complete free colonoscopy, and mailed invitation to use and return an enclosed fecal immunochemical test FOBT (FIT) kit—among a racially- and ethnically-diverse group of 5,970 uninsured individuals served by a large safety-net health system, not up to date with screening (30). Mailed invitations were supplemented by telephone calls to promote screening completion, and help with scheduling to complete colonoscopy for screening or diagnostic follow up of abnormal FIT. At one year, screening was significantly higher for FIT (40.7%) and colonoscopy outreach (24.6%) compared to usual care (12.1%), $p < 0.001$ for all comparisons. Among individuals with abnormal FIT, 82% completed diagnostic colonoscopy. Intervention effects were similar for non-Hispanic whites, non-Hispanic blacks, and Latinos. Importantly, the interventions were delivered through a safety-net health system that included a county-level sliding scale health assistance program that facilitated access to primary and specialty care (such as colonoscopy) within the health system – few such comprehensive systems exist in the US for underserved populations. Our results with mailed outreach are similar to others offering FOBT^(31, 32) or colonoscopy^(33, 34) outreach, thus suggesting that this approach is consistently effective for promoting screening completion compared to usual care.

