RCT inclusion/exclusion criteria. We will **include** individuals age 50 to 75 years, with one or more SYHC visits in the last year, at average-risk for CRC but not up-to-date with screening, insured by a MediCal provider, Medicare, or private health insurance. We will **exclude** individuals with personal history of CRC or colorectal polyps, as well as the uninsured. Uninsured individuals will be excluded because in absence of health insurance, we cannot guarantee that screening (and cancer care if CRC is found) will be financially possible. Inclusion and exclusion criteria will be applied through queries of the SYHC EHR.

Identification of candidate patients and recruitment. Using the SYHC EHR we will enroll and randomize 648 individuals meeting inclusion/exclusion criteria: 162 to usual care, inreach, mailed FIT outreach, and the

inreach strategy plus FIT outreach, respectively (see sample size and power calculations below). A waiver of documentation of informed consent will be obtained for randomization and intervention delivery based on two primary factors: 1) goal of increasing screening for as many individuals as possible, and 2) scientific advantage of observing as close to “real world” impact of the planned strategies on a sample of patients. We reviewed with our Institutional Review Board a potential strategy for complete waiver of informed consent, but were advised that maximizing patient autonomy and awareness of potential loss of confidentiality associated with research data collection merited at minimum a one-page informational research “fact sheet” that would provide patients with information about the research project. In the letter, patients will be the option to specifically note a desire not to participate in the intervention or subsequent data collection. Recruitment will continue until a sample size of 162 individuals per group who do not opt out of the research is achieved. In our primary, intent to screen analysis, we will analyze all randomized individuals who do not opt out of the research.

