The EHR will be queried 4 times over a 1 year period. At time of each query 1/4 of the target sample will be identified and randomized, and have the assigned interventions initiated. Each group will be followed for 12 months for the primary outcome: completion of any CRC screening test (guaiac fecal occult blood test, FIT, sigmoidoscopy, or colonoscopy), measured by evidence of screening documented within the EHR. Thus, the total recruitment period will last 12 months, and the duration through completion of 6 month follow up of all patients will be 24 months. Measurements will include demographic information (race, ethnicity, sex, and age), number and location of health center visits, primary provider, and comorbid medical conditions. In secondary analyses, we will determine whether screening rates vary across these characteristics, and also assess whether for significant interactions between characteristics and intervention effects.

Analytic approach and sample size, Aim 1. We estimated the sample size for 5 comparisons (usual care vs. inreach, usual care vs. outreach, usual care vs. inreach + outreach, inreach + outreach vs. outreach alone, and inreach + outreach vs. inreach alone), assuming $\alpha = 0.01$ across all groups and power ≥ 0.8 . For these assessments, we assumed the following rates of screening on follow up among individuals not up to date at baseline: 10% for usual care, 25% for inreach, 25% for outreach, 45% for inreach + outreach combined. The 10% rate for usual care and 25% estimate for outreach were conservative assumptions based on our previously cited work (30). The 25% rate for inreach was a conservative estimate based on observations that inreach interventions such as patient navigation have boosted screening completion (among patients referred for colonoscopy) by 41 to 78%. Finally, the 45% rate for both interventions combined was considered the minimal clinically significant difference that would justify implementing two different interventions for increasing screening. Under these assumptions, we computed need for a sample size of $n=648$ patients ($n=162$ for each group) to have sufficient power for all primary comparisons of interest.

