The primary outcome is completion of any CRC screening test (guaiac fecal occult blood test, FIT, sigmoidoscopy, or colonoscopy) within 12 months of randomization. The analytic approach taken will depend on whether or not an interaction exists between the outreach and inreach strategies on screening completion. If no interaction is present, screening rates for inreach vs. usual care and outreach vs. usual care will be compared using a Chi-square test of proportions, requiring $p < 0.01$ for statistical significance. If interaction is noted, we will compare screening rates with a Chi-square test of proportions for inreach without outreach vs. usual care, as well as inreach with outreach vs. usual care separately, using a $p < 0.025$ to indicate statistical significance. In both cases (interaction or no interaction), secondary comparisons will include inreach plus outreach vs. usual care, as well as inreach plus outreach vs. either strategy alone. We will conduct additional analyses treating screening completion as the dependent variable, and examine the relationship of group assignment, demographic characteristics, primary provider, and clinic visit frequency to this outcome. Factors associated with screening completion on univariate analyses will be considered as part of a logistic regression model examining factors independently associated with screening completion; in the case of interaction by group assignment a term for interaction will be included in our models. Additionally, interactions between other factors (e.g. gender, age, language preference, income, inreach strategy and frequency of clinic visits) will be considered.

Approach, Aim 2 Process Evaluation. Following the RE-AIM framework(41-43), a quasi-experimental process evaluation of intervention programs is proposed as part of the research protocol using validated measures developed in previous studies(44). This process evaluation is designed to examine the intervention’s acceptability, feasibility, and sustainability(45-47). Process measures include: intervention fidelity, recruitment and retention issues, dosage delivered and received, participant satisfaction, and *navigator* perceptions on areas for improvement in each one-on-one session. [name], [name], and [name] will lead trainings to ensure intervention fidelity and standardized intervention delivery and dosage.

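### The 10% usual-care rate is labelled conservative although the trial it is drawn from observed 12.1%; at that rate the single-arm test of inreach against usual care falls short of the stated power of at least 0.8

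*Combined protocol and SAP*

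**What the plan says.** The section on analytic approach and sample size for Aim 1 lists five pairwise comparisons, among them usual care vs inreach, at alpha 0.01 with the target "across all groups and power ≥ 0.8". The assumed screening rates are "10% for usual care, 25% for inreach, 25% for outreach, 45% for inreach + outreach combined". From these the plan arrives at 162 per group, 648 in total. It justifies two of the rates together: "The 10% rate for usual care and 25% estimate for outreach were conservative assumptions based on our previously cited work". The 25% for inreach has a separate basis, navigation studies, and is also called conservative.

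The Significance section reports the cited trial's one-year results as "FIT (40.7%) and colonoscopy outreach (24.6%) compared to usual care (12.1" percent. That trial enrolled uninsured patients.

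On testing, the same Aim 1 section says that without interaction "screening rates for inreach vs. usual care and outreach vs. usual care will be compared using a Chi-square test of proportions". The significance threshold in that branch is 0.01. If interaction is noted, inreach without outreach is compared with usual care at p < 0.025.

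**The concern.** A planning assumption is conservative when it makes the calculated power lower than the evidence suggests. In a superiority comparison with the intervention rate fixed, taking the control rate below the observed one does the reverse: it widens the assumed difference (15 points at 10%, 12.9 points at 12.1%) and slightly reduces the variance. One label covers two assumptions that err in opposite directions. The 25% for outreach lies well below the 40.7% observed; the 10% for usual care lies below the 12.1% observed in the same trial.

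What is at stake is how a null result for inreach alone would be read. The plan presents that comparison as having at least 80% power and shows no sensitivity to the usual-care rate. If the rate is what the plan's own source found, a null result is weaker evidence against inreach than the plan implies.

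**Working it through.** **Inputs.** From the Aim 1 sample-size section: usual care 10%, inreach 25%, 162 per arm, power 0.8, alpha 0.01 (0.025 in the interaction branch). From the Significance section: usual care 12.1%, FIT outreach 40.7%. Assumed because the plan does not say: two-sided tests. Continuity correction is not stated either, so both versions are shown.

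**Step 1: reproduce the plan's n.** With mean rate p̄ = (p1 + p2)/2 and difference d,

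n = [z(α/2)·√(2p̄(1−p̄)) + z(β)·√(p1(1−p1) + p2(1−p2))]² / d²

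For 10% vs 25%: p̄ = 0.175, d = 0.15, z values 2.576 and 0.842. The two terms are 1.384 and 0.443, so n = (1.827)²/0.0225 = 148.4, i.e. 149. The continuity-corrected size is

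n' = (n/4)·[1 + √(1 + 4/(n·d))]² = 161.5, i.e. **162**.

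This matches the plan exactly. The other comparisons need fewer: 142 corrected for 25% vs 45%, and 43 for 10% vs 45%. The 10% vs 25% comparisons therefore fix the sample size.

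**Step 2: power at 162 per arm.**

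Power = Φ{[d − z(α/2)·√(2p̄(1−p̄)/n)] / √([p1(1−p1) + p2(1−p2)]/n)}, with d reduced by 1/n for the corrected version.

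At 10% vs 25%, alpha 0.01: (0.150 − 2.576 × 0.04222)/0.04139 = 0.997, power 0.84. Corrected: 0.848, power 0.80.

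At 12.1% vs 25%, alpha 0.01: p̄ = 0.1855, d = 0.129; (0.129 − 2.576 × 0.04319)/0.04259 = 0.417, power 0.66. Corrected: 0.272, power 0.61. Exact enumeration of the chi-square test agrees (0.668 and 0.612).

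| Usual care vs inreach alone | alpha 0.01 | alpha 0.025 |
|---|---|---|
| 10% vs 25% | 0.84 (0.80 corrected) | 0.91 (0.88) |
| 11% vs 25% | 0.76 (0.72) | 0.85 (0.82) |
| 12.1% vs 25% | 0.66 (0.61) | 0.775 (0.73) |
| 12.1% vs 27.1% (15-point gain kept) | 0.80 (0.76) | 0.88 (0.85) |

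At alpha 0.01, uncorrected power drops below 0.80 once usual care passes about 10.5%. With the correction that yields 162, it does so just above 10%.

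**Step 3: detectable rate.** With usual care at 12.1%, 162 per arm and alpha 0.01, 80% power requires an inreach rate of 27.1% (27.8% corrected).

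**Step 4: what is not affected (alpha 0.01, usual care 12.1% where it enters).**

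- Outreach at 40.7% vs usual care: above 0.99.
- Combination at 45% vs usual care: above 0.99.
- Combination at 45% vs either strategy at 25%: 0.89 (0.87 corrected); the usual-care rate does not enter.
- Both inreach arms pooled, mean (25% + 45%)/2 = 35%, 324 patients vs 162 on usual care: above 0.99.
- Factorial margin, 324 vs 324, 35% vs (12.1% + 25%)/2 = 18.55%: 0.99.

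**The case against.** Several points on the other side stand and limit the finding.

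**Hypothesis 1a.** A reader might infer that the main inreach hypothesis is underpowered. The documents do not support that. Hypothesis 1a covers inreach with or without FIT outreach, and in that pooled form power stays at about 0.99, given the plan's 45% for the combination. The shortfall concerns inreach alone, which the plan does list among its sizing comparisons and does test in the interaction branch.

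**Threshold.** The 0.66 applies at alpha 0.01. The branch that explicitly names inreach without outreach uses 0.025, where power is 0.775 (0.73 corrected). The no-interaction branch does not say whether its inreach comparison is single-arm or pooled. Both thresholds therefore belong in the restatement; neither gives 0.8 at 12.1% vs 25%.

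**Margin in the inreach rate.** It is tempting to say inreach has no cushion at all. The plan calls its 25% conservative too, citing navigation gains of 41 to 78% among patients referred for colonoscopy, and the Significance section mentions inreach increases of 17%, 19% and 25%. The text does not settle whether these are percentage points or relative gains. If the smallest, 17%, is in points, inreach would be 12.1 + 17 = 29.1%, and power at 29% is 0.89. If the gains are relative, even 78% gives only 12.1 × 1.78 = 21.5%, below 25%. The margin is unestablished rather than absent.

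**Direction of the true rate.** A reader might infer that usual care will exceed 12.1%, because this trial drops the uninsured ("Uninsured individuals will be excluded because in absence of health insurance") and the Specific Aims put screening rates "among uninsured and those insured by Medicaid are just 20 and 25%, respectively". Those are screening rates by insurance group, not new completion among people who are not up to date, so they do not set the usual-care rate here. The Overview also gives a 6-month outcome window, against 12 months in the Aim 1 analysis section. The 12.1% is a one-year figure, and a 6-month rate could be lower. The rate could fall on either side.

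**Sample size.** The 162 is not a miscalculation; it follows exactly from the stated inputs.

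**Conclusion.** The label is wrong for the usual-care rate. Against the plan's own source, 10% favours the design, and only the 25% for outreach is conservative. Because 162 per group is just enough for 10% vs 25%, the single-arm comparison of inreach with usual care has almost no room for a higher control rate. At 12.1% its power is 0.66 (0.61 corrected) at alpha 0.01 and 0.775 (0.73 corrected) at 0.025, instead of at least 0.8.

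This rests on two-sided tests, 162 analysed per arm, inreach held at 25%, and 12.1% carrying over from the cited trial. Outreach vs usual care would have the same power if outreach were also only 25%, but the source gives 40.7%. The finding does not extend to the pooled Hypothesis 1a or to the comparisons involving the combination. It should be corrected because readers will rely on the stated power when interpreting a null result for inreach alone.

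**What to change.** In the Aim 1 sample-size paragraph:

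1. Remove the description of the usual-care rate as conservative, keep it for outreach, and state that the cited trial observed 12.1%.
2. Give power for inreach alone vs usual care over usual-care rates of 10% to 12.1%, with inreach at 25%: 0.84 to 0.66 uncorrected and 0.80 to 0.61 corrected at alpha 0.01; 0.91 to 0.775 uncorrected and 0.88 to 0.73 corrected at 0.025.
3. State that with usual care at 12.1% the inreach rate detectable with 80% power at alpha 0.01 is about 27-28%.
4. Note that the true usual-care rate could be above or below 12.1%, because the cited trial enrolled uninsured patients and the outcome window is given as both 6 and 12 months.

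The cost is one paragraph of wording and a less favourable power statement for one comparison. No extra patients and no change to the analysis are needed.

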Despite potential opportunities to deliver screening for underserved populations through FQHCs, many challenges exist. Available strategies for screening promotion have undergone limited development and evaluation among low income predominantly Spanish-speaking FQHC Latino patients. Further, it is unclear which strategies are best for increasing screening, and whether implementing multiple approaches (e.g. inreach delivered at point of a medical visit vs. outreach not requiring an in-person visit) would be superior to taking one approach alone for optimizing screening rates. To begin to address these challenges, we have conducted pilot work that has 1) established an academic-community CRC partnership between UCSD, SDSU, and SYHC; 2) established that FQHCs are keenly interested in understanding the best and most practical strategies for screening promotion; 3) identified (through key informant interviews of providers, clinic leadership, experienced *promotoras* (community health workers), and screening experts) key themes our interventions must address; 4) adapted previous effective materials used for mailed FIT outreach and patient navigation-based in-reach for screening promotion. Now, utilizing this comprehensive partnership and pilot work, we propose the following specific aims:

Aim 1: Among 648 Latinos age 50-75 years served by the SYHC FQHC, not up-to-date with screening, compare impact of 4 strategies on screening completion via a randomized controlled trial. The strategies will include: a) a patient-navigation-based, in clinic, inreach strategy, b) a mailed FIT outreach strategy (FIT outreach), c) inreach + FIT outreach, and d) usual care (n=162 per group).

Hypothesis 1a: *The inreach strategy (with or without FIT outreach) will be significantly superior to usual care*

Hypothesis 1b: *FIT outreach (with or without the inreach strategy) will be significantly superior to usual care*

Hypothesis 1c: *FIT outreach + the inreach strategy will be significantly superior to either strategy alone compared to usual care.*

Aim 2: Conduct a process evaluation to examine the interventions' reach, effectiveness, acceptability, feasibility, and sustainability following the RE-AIM framework.

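### The no-interaction primary tests do not say which arms form inreach and outreach; if both inreach arms are pooled against usual care, outreach's effect is credited to inreach

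*Combined protocol and SAP*

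**What the plan says.** Specific Aims sets out four randomized arms: inreach, FIT outreach, the two combined, and "d) usual care (n=162 per group"). This is a 2x2 factorial with usual care as the cell that receives neither strategy.

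The hypotheses in Specific Aims are worded across the factorial:
- 1a: "The inreach strategy (with or without FIT outreach) will be significantly superior to usual care"
- 1b: "FIT outreach (with or without the inreach strategy) will be significantly superior to usual care"

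Under Analytic approach and sample size, Aim 1, the primary test depends on whether the two strategies interact. Without interaction: "If no interaction is present, screening rates for inreach vs. usual care and outreach vs. usual care will be compared" by chi-square, "requiring $p < 0.01$ for statistical significance". With interaction, inreach is separated into without and with outreach, and each part is tested against usual care at 0.025. In both branches, the combined arm against usual care and against each single strategy are secondary comparisons.

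The sizing paragraph of the same section lists five comparisons of one arm with another. It assumes α = 0.01 "across all groups and power ≥ 0.8" and rates of "10% for usual care, 25% for inreach, 25% for outreach, 45% for inreach + outreach combined".

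No primary test compares a strategy with all patients not given it, and none adjusts for the other strategy. The logistic model is described only as an additional analysis.

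**The concern.** The word inreach in the no-interaction branch can be taken in two ways.

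- **Pooled (324 vs 162).** Hypothesis 1a counts patients with or without outreach as inreach patients. The plan separates those two groups only when interaction is noted, which implies that they are otherwise combined.
- **Single arm (162 vs 162).** The recruitment section uses inreach as the name of one randomized arm. The sizing paragraph uses it in the same way, with the same 0.01 level.

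The choice matters because the pooled test does not isolate inreach: its two groups also differ in exposure to outreach. An inreach programme that adds nothing could be reported as effective in the primary analysis. The Significance section says that health centers are unsure which approach deserves limited resources, and a test that transfers one strategy's effect to the other cannot settle that. Outreach has the same problem in mirror image.

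**Working it through.** **Inputs.** 162 per arm; p < 0.01, taken as two-sided (the plan does not state sidedness, but two-sided reproduces its N); planning rates 10/25/25/45% for usual care, inreach, outreach and combined. The earlier mailed-outreach trial described under Significance gives 12.1% for usual care and 40.7% for FIT outreach. Rates below are always in that arm order.

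**1. The plan's own N.** For 10% vs 25%, with mean rate 0.175:

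n = [2.576·√(2·0.175·0.825) + 0.842·√(0.10·0.90 + 0.25·0.75)]² / 0.15² = 1.8275² / 0.0225 = 148.4

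With continuity correction: (148.4/4)·[1 + √(1 + 4/(148.4·0.15))]² = 161.5, so 162. This matches the plan. For 25% vs 45% the same method gives 142, and for 10% vs 45% it gives 43. N is therefore driven by a single-arm comparison with usual care.

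**2. What the pooled test estimates.** Let inreach add *a* and outreach add *b* percentage points, with no interaction on that scale. Then

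(inreach-only + combined)/2 − usual care = *a* + *b*/2.

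With *a* = *b* = 15 the pooled test estimates 22.5 points against a true 15. With *a* = 0 and *b* = 15 it estimates 7.5 points against a true 0.

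**3. False declaration when inreach is inert (10/10/25/25%).** The pooled inreach rate is 0.175 and usual care 0.10, so d = 0.075. The overall rate is (324·0.175 + 162·0.10)/486 = 0.15.

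- SE under the null: √[0.15·0.85·(1/324 + 1/162)] = 0.0344
- SE under the alternative, using the mean within-arm variance (0.09 + 0.1875)/2 = 0.13875: √(0.13875/324 + 0.09/162) = 0.0314
- Probability of rejection: Φ[(0.075 − 2.576·0.0344)/0.0314] = Φ(−0.43) = 33%

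Simulation (400,000 trials per scenario, chi-square without continuity correction):

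| True rates, inreach inert | Pooled 324 vs 162 | CMH stratified by outreach |
|---|---|---|
| 10/10/20/20% (assumption) | 13% | 1.0% |
| 10/10/25/25% (planning rates for usual care and outreach) | 34% | 1.0% |
| 12.1/12.1/40.7/40.7% (cited trial) | 88% | 1.0% |

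**4. Does the interaction check protect?** No. An inert inreach produces no interaction, so these trials enter this branch. Among simulated trials that pass a two-sided 0.05 interaction test on the risk-difference scale (an assumption; the plan gives no test, scale or level), the false declaration rate is still 34%.

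The branch is also likely to be used under the planning rates. The interaction there is 45 − 25 − 25 + 10 = 5 points, with SE √[(0.09 + 0.1875 + 0.1875 + 0.2475)/162] = 6.6 points, so the same test has about 12% power.

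**5. The single-arm reading.** Type I error is held at 1%. Power at 10% vs 25% is 0.84 by the normal approximation and 0.85 by simulation. With additive effects (10/25/25/40%), the stratified test of 324 vs 324 has power 0.97. The SE of the inreach effect is √[(0.09 + 0.1875)/162] = 4.1 points for the single-arm test and ½·√[(0.09 + 0.1875 + 0.1875 + 0.24)/162] = 3.3 points for the marginal one.

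**6. Where the marginal test does worse.** With sub-additive rates 10/25/25/30% (an assumption), the interaction test assumed in step 4 misses the interaction in 66% of trials. The stratified marginal test then has power 0.69 against 0.85 for the single-arm test (powers not conditioned on the interaction result).

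**The case against.** The strongest reply is that the plan never states a comparison of 324 with 162. Its arm labels and sizing paragraph treat inreach as one arm of 162, and the no-interaction branch repeats the labels and the level used there. On that reading nothing is invalid: the error rate is correct, the power target is met, and the result does not depend on the no-interaction premise, which the trial can check only weakly. All of this stands. It does not remove the ambiguity, because hypotheses 1a and 1b and the split in the interaction branch point the other way.

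A second reply is that the planned comparison of the combined arm with outreach alone would expose an inert inreach. That is correct: at 10/10/25/25% it favours the combination in only 0.5% of trials. But it is secondary, so it would sit beside a positive primary claim without preventing it.

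A third is that usual care may be shorthand for not receiving inreach. That would be the correct marginal test, but the document uses the term for the fourth arm, so the text would still need changing.

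A reader might go further and infer that both readings are inferior to the marginal comparison, or that the single-arm test discards half the data for no reason. The documents do not support this. The other arms are used in the interaction assessment and the secondary comparisons, and step 6 shows the single-arm test ahead when effects are clearly sub-additive.

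**Conclusion.** The concern holds as a defect in the definition of the primary test, with a serious consequence on one reading that the text supports. If the inreach arms are pooled against usual care, an inert inreach is declared effective in about 34% of trials at the planning rates for usual care and outreach. The figure is 13% if outreach reaches only 20% and about 88% at the cited trial's rates; the nominal rate is 1%. These figures assume a two-sided 0.01 level, 162 analysed per arm and an inreach effect of exactly zero.

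On the single-arm reading there is no bias. The cost is efficiency when effects are close to additive: power 0.85 instead of 0.97 at 10/25/25/40%.

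It would be wrong to infer that the sample size is in error, since 162 per group reproduces exactly. It would also be wrong to infer that the plan certainly pools: the text leaves this open, and that is the fault to correct.

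**What to change.** 1. In Analytic approach and sample size, Aim 1, name the arms and numbers in each no-interaction primary test, and state that pooled inreach or pooled outreach arms will not be compared with usual care unadjusted.
2. Since this branch presumes no interaction, compare all inreach (inreach-only + combined, 324) with all non-inreach (outreach-only + usual care, 324) by a Cochran-Mantel-Haenszel test stratified by outreach. Do the same for outreach, stratified by inreach.
3. Reword hypotheses 1a and 1b as each strategy against not receiving that strategy, and align the sizing paragraph.
4. Always report the single-arm comparisons with usual care beside the marginal results.
5. State the scale on which interaction is judged. Rates of 10/25/25/40% are additive in percentage points, but the inreach odds ratio is (0.25/0.75)/(0.10/0.90) = 3.0 without outreach and (0.40/0.60)/(0.25/0.75) = 2.0 with it.

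If the sponsor prefers to keep the single-arm tests as primary, naming them explicitly as 162 vs 162 also removes the bias; hypotheses 1a and 1b should then be reworded to match.

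**Cost.** No extra patients or data; the change is to wording. The marginal option does change the estimand, from a contrast with current practice to an average over the presence and absence of the other strategy. It also loses power if effects are sub-additive and the interaction is missed (0.69 vs 0.85 at 10/25/25/30%). The plan should state both.
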